**Events Meeting the AE Definition**

---

- Exacerbation of a chronic or intermittent pre-existing condition including either an increase in frequency and/or intensity of the condition.
- New conditions detected or diagnosed after study intervention administration even though it may have been present before the start of the study.
- Signs, symptoms, or the clinical sequelae of a suspected drug-drug interaction.
- Signs, symptoms, or the clinical sequelae of a suspected overdose of either study intervention or a concomitant medication. Overdose per se will not be reported as an AE/SAE unless it is an intentional overdose taken with possible suicidal/self-harming intent. Such overdoses should be reported regardless of sequelae.
- The signs, symptoms, and/or clinical sequelae resulting from lack of efficacy will be reported as AE or SAE if they fulfil the definition of an AE or SAE. Also, “lack of efficacy” or “failure of expected pharmacological action” also constitutes an AE or SAE.

---

---

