**Table 1-1 Study Schedule of Activities (SoA)**

Procedures	Screening a	Baseline Pre-dose	ED 10-15	ED 50-75 Every 6 months			End of study 100 ED / Early Termination
	Visit 1 2-8 Wks before baseline	Visit 2 Day 1	Visit 3 Wk 8-10 b	Visit 4 Month 6 (±14 days) c	Visit 5 Month 12 (±14 days) c	Visit 6 Month 18 if needed (±14 days) c	Last Visit (+14 days)
Recovery (pre and 15-30 min post injection FVIII levels) h		X	X				X
FVIII level after 48 or 72 hours after last injection				X	X		
In-hospital injection of Jivi		X	X				X
AE review	X	X	X	X	X	X	X
Return used and unused study intervention			X	X	X	X	X
Dispense study intervention for home injections			←==continuously in accordance with IxRS drug dispensing schedule==→				
Injection of Jivi			←=====continuously in accordance with assigned treatment regimen=====→				
Concomitant medication review	X		←=====continuously=====continuously=====→				
Patient diary (EPD) documentation	X		←=====continuously=====continuously=====→				
Interaction between participants and investigators			←=====Monthly contact=====→				

Abbreviations: ADA=anti-drug antibody, AE=adverse event, ALT=alanine aminotransferase, AST=aspartate aminotransferase, ED=exposure days, EPD=electronic patient diary, HIV=human immunodeficiency virus, hrs=hours, IxRS=Interactive voice/web response system, max=maximum, and Wk=week.

- The time interval between Screening and Baseline visit is 2 to 8 weeks.
- Although the allowable visit window is ±14 days, visits must occur within the specified ED range.
- Visits should be scheduled within the visit window so that at least one visit occurs in the 50 – 75 ED range.
- HIV screening will be performed only in case that negative result in patient documentation is older than 1 year at date of screening.
- Only in case of Early Termination Visit before V6.
- In case of any injection related AE, vital signs will be collected in addition post-injection for participants.
- At Baseline, Visit 3 and End of Study/Early Termination Visit, blood samples for immunogenicity will be collected before the in-hospital injection of Jivi.
- Recovery should be measured at least 72 h after last injection of FVIII of Jivi.

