### 8.3.1 Time Period and Frequency for Collecting AE and SAE Information

All AEs and SAEs will be collected from the signing of the informed consent form (ICF) until the end of the final study visit at the time points specified in the SoA (Section [1.3](#)).

Medical occurrences that begin before obtaining informed consent but are diagnosed at screening or during the screening period (e.g., abnormal lab values) will be recorded on the Medical History/Current Medical Conditions section of the case report form (CRF), not the AE section.

All SAEs will be recorded and reported to the sponsor or designee immediately and under no circumstances should this exceed 24 hours, as indicated in Section [10.3](#). The investigator will submit any updated SAE data to the sponsor within 24 hours of it being available.

Investigators are not obligated to actively seek AE or SAE after conclusion of the study participation. However, if the investigator learns of any SAE, including a death, at any time after a participant has been discharged from the study, and he considers the event to be reasonably related to the study intervention or study participation, the investigator must promptly notify the sponsor.

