## 10.3 Appendix 3: Adverse Events: Definitions and Procedures for Recording, Evaluating, Follow-up, and Reporting

### 10.3.1 Definition of AE

#### AE Definition

In a clinical study, an AE is any untoward medical occurrence (ie, any unfavorable and unintended sign [including abnormal laboratory findings], symptom or disease) in a subject or clinical investigation subject after providing written informed consent for participation in the study. Therefore, an AE may or may not be temporally or causally associated with the use of a medicinal (investigational) product.

A surgical procedure that was planned prior to the start of the study by any physician treating the subject should not be recorded as AE (however, the condition for which the surgery is required may be an AE).

In the following differentiation between medical history and AEs, the term “condition” may include abnormal, eg, physical examination findings, symptoms, diseases, laboratory values.

- Conditions that started before signing of informed consent and for which no symptoms or treatment are present until signing of informed consent are recorded as medical history (eg, seasonal allergy without acute complaints, abnormal laboratory finding at screening).
- Conditions that started before signing of informed consent and for which symptoms or treatment are present after signing of informed consent, at unchanged intensity, are recorded as medical history (eg, allergic pollinosis).
- Conditions that started or deteriorated after signing of informed consent will be documented as adverse events.

**Note:** Any bleeding event occurring during the study will not be documented as an AE, because this event is captured in the assessment of efficacy. However, if the bleed requires hospitalization or fulfills another seriousness criterion, it must be reported as a Serious Adverse Event (SAE) (Section 10.3.2).

Bleeding events treated with Jivi and recorded in the EPD do not need to be documented as AEs because they are already captured. However, occurrence of traumatic injury and other bleeds should follow standard AE reporting procedures. Any bleed requiring hospitalization or fulfilling another seriousness criterion must be reported as a SAE (Section 10.3.2).

---

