#### Assessment of Intensity

- The investigator will make an assessment of intensity for each AE and SAE reported during the study and assign it to 1 of the following categories:
- Mild: An event that is easily tolerated by the participant, causing minimal discomfort and not interfering with everyday activities.
- Moderate: An event that causes sufficient discomfort and interferes with normal everyday activities.
- Severe: An event that prevents normal everyday activities. An AE that is assessed as severe should not be confused with an SAE. Severe is a category utilized for rating the intensity of an event; and both AEs and SAEs can be assessed as severe.
- An event is defined as 'serious' when it meets at least 1 of the predefined outcomes as described in the definition of an SAE, NOT when it is rated as severe.

---

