### Follow-up of AEs and SAEs

---

- The investigator is obligated to perform or arrange for the conduct of supplemental measurements and/or evaluations as medically indicated or as requested by the Sponsor to elucidate the nature and/or causality of the AE or SAE as fully as possible. This may include additional laboratory tests or investigations, histopathological examinations, or consultation with other health care professionals.
- New or updated information will be recorded in the originally completed CRF.
- The investigator will submit any updated SAE data to the Sponsor within 24 hours of receipt of the information.

---

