### **6.4 Safety**

All safety analyses will be performed on the SAF. MedDRA codes of studies 13024 and 15912 will be updated by the MedDRA version used for study 19764. An AE will be considered treatment-emergent if it starts after first injection and not later than 7 days after last injection of Jivi.

Overview tables displaying all AEs, all pre-treatment AEs and all treatment emergent adverse events (TEAEs) will be created. All subsequent tables will be presented by MedDRA preferred term (PT) and system organ class (SOC). Serious AEs, TEAEs, serious TEAEs, drug-related TEAEs, serious drug-related TEAEs, TEAEs of special interest, TEAEs causing discontinuation of study drug, TEAEs by maximum intensity, drug-related TEAEs by maximum intensity, non-serious TEAEs, and AEs leading to death will be presented.

Overview tables, all TEAEs, serious TEAEs, drug-related TEAEs and serious drug-related TEAEs will be displayed by subgroups.

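### The TEAE rule looks only at the start date, so an AE that begins in screening and worsens on Jivi may be missing from the TEAE tables, depending on how the site records it

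*Protocol*

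**What the plan says.** Protocol 10.3.1 treats worsening as an adverse event in two places. The definition states: "Conditions that started or deteriorated after signing of informed consent will be documented as adverse events". The list of qualifying events includes "Exacerbation of a chronic or intermittent pre-existing condition including either an increase in frequency and/or intensity of the condition".

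The treatment-emergent rule has the same wording in protocol 9.4.2 and SAP 6.4: "An AE will be considered treatment-emergent if it starts after first injection and not later than 7 days after last injection of Jivi". Neither document adds a clause for worsening.

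Protocol 8.3.1 sets the collection window: "All AEs and SAEs will be collected from the signing of the informed consent form (ICF) until the end of the final study visit". A footnote to the Schedule of Activities adds: "The time interval between Screening and Baseline visit is 2 to 8 weeks". Pre-treatment AEs are therefore expected, and SAP 6.4 plans for them: "Overview tables displaying all AEs, all pre-treatment AEs and all treatment emergent adverse events (TEAEs) will be created".

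On recording, protocol 10.3.3 tells the investigator to assess the intensity of each AE and "assign it to 1 of the following categories". Under follow-up it says: "New or updated information will be recorded in the originally completed CRF". No section says whether an increase in intensity updates the existing entry or opens a new one.

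**The concern.** TEAEs are a secondary endpoint under the primary safety objective. The AE definition counts deterioration, while the TEAE rule reads only a start date. The link between them is the recording convention, and the plan does not state it.

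Suppose a site follows the follow-up instruction literally. An AE that was mild in screening and becomes severe, serious or drug-related on Jivi then stays one record with a start date before the first injection. The rule classes it as pre-treatment. It drops out of the tables of all TEAEs, serious TEAEs, drug-related TEAEs, TEAEs of special interest, TEAEs causing discontinuation and TEAEs by maximum intensity.

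Relative to the protocol's own AE definition, such an omission can only lower the TEAE count. Two sites that both comply with the protocol could also classify the same clinical course differently.

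**Working it through.** The plan states no figure on this point, so the check is mainly a comparison of rules. The arithmetic gives scale only.

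**Which events are exposed**

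1. *Condition present before consent.* Under 8.3.1 and 10.3.1 it is medical history. If it deteriorates on Jivi, 10.3.1 makes the deterioration an AE. There is no earlier AE record to update, so it is a new entry, and a TEAE if dated at the worsening.
2. *AE starting within the TEAE window.* It is a TEAE whether or not it worsens.
3. *AE starting between consent and first injection, worsening on Jivi.* Two recordings are compatible with the protocol:
   - The existing entry is updated (10.3.3). The start date stays in screening, and the event is not a TEAE.
   - The exacerbation is entered as its own AE (10.3.1) with an on-treatment start date, and it is a TEAE.

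Only the third case is exposed.

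**What other rules do with it**

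- The imputation rule in SAP 4.3 moves an incomplete start date to the first treatment day when that day lies in the possible range. It does not act on a complete screening date, so it does not help here.
- SAP 6.4 also tabulates Serious AEs and AEs leading to death without limiting them to TEAEs, and gives all-AE and pre-treatment overviews. Protocol 9.4.2 lists every AE with start, duration, severity and relation to drug. The event therefore stays visible outside the TEAE tables.

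**Share of AEs that could start in screening** (assumptions: onset uniform over time, full adherence, no extra exposure days (ED) for bleeds, participant reaches 100 ED)

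- Inputs: screening 2 to 8 weeks; every 5 days until Visit 3 at week 8 to 10 (about day 57 to 71); then twice weekly (3.5 days per ED) or every 7 days.
- ED by Visit 3: 12 at day 57, 15 at day 71. Remaining: 100 − 12 = 88, or 100 − 15 = 85.
- Twice weekly: 57 + 88 × 3.5 = day 365; 71 + 85 × 3.5 = day 368.5. This is about 52 to 53 weeks.
- Every 7 days: 71 + 85 × 7 = day 666; 57 + 88 × 7 = day 673. This is about 95 to 96 weeks.
- Smallest share: 2 / (2 + 96) = 2.0%. Largest share: 8 / (8 + 52) = 13.3%.

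Only those AEs that go on to worsen on Jivi are affected, and the documents give no rate for that. Participants who stop before 100 ED would have a larger screening share than this range.

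**Effect of one participant on TEAE incidence**

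- With 30 treated: 1/30 = 3.3 points. With 25 treated: 1/25 = 4.0 points.
- In the pool of protocol 9.2 (134 + 73 + 25 = 232): 1/232 = 0.4 points.

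These shifts occur only if the participant has no other TEAE.

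**The case against.** The best counter-argument is that the protocol already captures the event. Section 10.3.1 makes the exacerbation itself an AE, so an exacerbation on Jivi is an AE that starts after the first injection and meets the TEAE rule. The follow-up instruction in 10.3.3 is general, does not mention intensity and does not forbid a new entry. One intensity category per AE fits equally well with opening a new record. CRF completion instructions, which might settle the matter, are not among the documents.

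This stands in part. A reader might infer that an AE beginning in screening can never become a TEAE. The documents do not support that, because a separate entry dated at the worsening is a legitimate reading. A reader might also infer that on-treatment severity would be tabulated in a pre-treatment column. SAP 6.4 plans intensity tables only for TEAEs and drug-related TEAEs, so that does not follow either.

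The consequences are also limited. Serious and fatal events stay in their own tables, and with 25 to 30 participants a listing would show the case. The inhibitor and antibody endpoints are analysed from laboratory results and do not depend on this rule. The events of special interest (hypersensitivity to Jivi and loss of its efficacy) would hardly begin before the first injection, so that table is exposed mainly in principle.

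What the objection does not remove is the dependence of a secondary safety endpoint on an unstated recording convention. The only instruction on updated information points towards the original record.

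A last objection concerns the remedy. SAP 4.1 requires data handling consistent with 13024 and 15912, and the pooled safety analysis is the regulatory purpose of the study. A new definition could put two TEAE definitions in the same tables. That is a real cost, and the fix allows for it.

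**Conclusion.** The gap is real and narrow. The TEAE rule uses the start date alone, and the plan does not say how a post-injection worsening of a screening AE is recorded. Such an event may therefore be missing from the TEAE tables. The effect runs in one direction, towards fewer TEAEs, and applies only to AEs that start between consent and first injection and then worsen on Jivi.

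Its size cannot be fixed from the documents. The 2% to 13% is a ceiling on the affected share of AEs for participants who reach 100 ED, and it rests on the uniform-onset assumption. The 3.3 to 4.0 points per participant hold only where no other TEAE occurs during a follow-up that may last 1 to 2 years. This does not threaten the primary endpoint. It is worth correcting because the correction is cheap and makes the endpoint independent of site practice.

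**What to change.** 1. In protocol 9.4.2 and SAP 6.4, define a TEAE for study 19764 as an AE that starts, or increases in intensity or becomes serious, after the first injection and not later than 7 days after the last.
2. In protocol 10.3.3 and the CRF instructions, require that a pre-treatment AE that worsens after the first injection be entered as a new record, with the date of worsening as its start date. This gives the definition a date to act on, and it also covers an increase in frequency, which 10.3.1 counts as an AE.
3. For the pooled tables, check the rule used in 13024 and 15912, whose plans are cited but not included here. If their data cannot show worsening, keep the start-date rule in the pooled column and footnote the difference.

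The cost is one sentence in each document, a CRF completion instruction and possibly a footnote. The downside is a slightly higher TEAE count in 19764 and possibly two TEAE definitions side by side in the same tables.

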**Events NOT Meeting the AE Definition**

---

- Any clinically significant abnormal laboratory findings or other abnormal safety assessments which are associated with the underlying disease, unless judged by the investigator to be more severe than expected for the participant’s condition.
- The disease/disorder being studied or expected progression, signs, or symptoms of the disease/disorder being studied, unless more severe than expected for the participant’s condition.
- Medical or surgical procedure (e.g., endoscopy, appendectomy): the condition that leads to the procedure is the AE.
- Situations in which an untoward medical occurrence did not occur (social and/or convenience admission to a hospital).
- Anticipated day-to-day fluctuations of pre-existing disease(s) or condition(s) present or detected at the start of the study that do not worsen.
- Any bleeding event occurring during the study will not be documented as an AE, because this is captured in the assessment of efficacy. However, if the bleed fulfills the criterion for an SAE (e.g. results in hospitalization), then the event should be recorded and reported as an SAE.

---

### 10.3.2 Definition of SAE

---

**An SAE is defined as any untoward medical occurrence that, at any dose:**

---

**a. Results in death**

---

**b. Is life-threatening**

- The term 'life-threatening' in the definition of 'serious' refers to an event in which the participant was at risk of death at the time of the event. It does not refer to an event, which hypothetically might have caused death, if it were more severe.

---

**c. Requires inpatient hospitalization or prolongation of existing hospitalization**

A hospitalization or prolongation of hospitalization will not be regarded as an SAE if at least one of the following exceptions is met:

- The admission results in a hospital stay of less than 12 hours
- The admission is pre-planned  
(ie, elective or scheduled surgery arranged prior to the start of the study)
- The admission is not associated with an AE  
(eg, social hospitalization for purposes of respite care).

However, it should be noted that invasive treatment during any hospitalization may fulfill the criterion of 'medically important' and as such may be reportable as an SAE dependent on clinical judgment. In addition, where local regulatory authorities specifically require a more stringent definition, the local regulation takes precedence.

---

**d. Results in persistent disability/incapacity**

- The term disability means a substantial disruption of a person's ability to conduct normal life functions.
- This definition is not intended to include experiences of relatively minor medical significance such as uncomplicated headache, nausea, vomiting, diarrhea, influenza, and accidental trauma (e.g., sprained ankle) which may interfere with or prevent everyday life functions but do not constitute a substantial disruption.

---

**e. Is a congenital anomaly/birth defect**

---

**f. Is another medically important serious event as judged by the investigator.**

- Medical or scientific judgment should be exercised in deciding whether SAE reporting is appropriate in other situations such as important medical events that may not be immediately life-threatening or result in death or hospitalization but may jeopardize the participant or may require medical or surgical intervention to prevent one of the other outcomes listed in the above definition. These events should usually be considered serious.
- Examples of such events include invasive or malignant cancers, intensive treatment in an emergency room or at home for allergic bronchospasm, blood dyscrasias or convulsions that do not result in hospitalization, or development of drug dependency or drug abuse.

---

### 10.3.3 Recording and Follow-Up of AE and/or SAE

---

#### AE and SAE Recording

- When an AE/SAE occurs, it is the responsibility of the investigator to review all documentation (e.g., hospital progress notes, laboratory reports, and diagnostics reports) related to the event.
- The investigator will then record all relevant AE/SAE information in the CRF.
- It is not acceptable for the investigator to send photocopies of the participant's medical records to Study Monitor/Medical Monitor in lieu of completion of the AE/SAE CRF page.
- There may be instances when copies of medical records for certain cases are requested by the Sponsor. In this case, all participant identifiers, with the exception of the participant number, will be redacted on the copies of the medical records before submission to the Sponsor.
- The investigator will attempt to establish a diagnosis of the event based on signs, symptoms, and/or other clinical information. Whenever possible, the diagnosis (not the individual signs/symptoms) will be documented as the AE/SAE.

---

#### Assessment of Intensity

- The investigator will make an assessment of intensity for each AE and SAE reported during the study and assign it to 1 of the following categories:
- Mild: An event that is easily tolerated by the participant, causing minimal discomfort and not interfering with everyday activities.
- Moderate: An event that causes sufficient discomfort and interferes with normal everyday activities.
- Severe: An event that prevents normal everyday activities. An AE that is assessed as severe should not be confused with an SAE. Severe is a category utilized for rating the intensity of an event; and both AEs and SAEs can be assessed as severe.
- An event is defined as 'serious' when it meets at least 1 of the predefined outcomes as described in the definition of an SAE, NOT when it is rated as severe.

---

#### Assessment of Causality

- The investigator is obligated to assess the relationship between study intervention and each occurrence of each AE/SAE.
- A "reasonable possibility" of a relationship conveys that there are facts, evidence, and/or arguments to suggest a causal relationship, rather than a relationship cannot be ruled out.
- The investigator will use clinical judgment to determine the relationship.
- Alternative causes, such as underlying disease(s), concomitant therapy, and other risk factors, as well as the temporal relationship of the event to study intervention administration will be considered and investigated.

---

---

- The investigator will also consult the Investigator's Brochure (IB) and/or Product Information, for marketed products, in his/her assessment.
- For each AE/SAE, the investigator **must** document in the medical notes that he has reviewed the AE/SAE and has provided an assessment of causality.
- There may be situations in which an SAE has occurred, and the investigator has minimal information to include in the initial report to the Sponsor. However, **it is very important that the investigator always make an assessment of causality for every event before the initial transmission** of the SAE data to the Sponsor.
- The investigator may change his/her opinion of causality in light of follow-up information and send an SAE follow-up report with the updated causality assessment.
- The causality assessment is one of the criteria used when determining regulatory reporting requirements.

---

